18.7 STATISTICAL POWER

The primary endpoint (change in ischemic burden) can be as a continuous or a dichotomous endpoint. The advantage of the continuous endpoint is that it requires a smaller sample size to reach statistical significance. The disadvantage with this approach, however, is the inability to easily account for those patients who require revascularization or die prior to repeat perfusion imaging. For example, a patient who develops ischemia at two years and receives bypass surgery may have a normal three year perfusion image. One method for handling patients undergoing interval revascularization would be to attempt a repeat perfusion image prior to revascularization. If this is not clinically feasible, we could assign a standardized perfusion deduction based upon the number of diseased vessels revascularized.

Alternatively, one could use a dichotomous approach, defining a successful therapy as one which prevented both the progression of ischemic territory or the occurrence of clinical endpoints (e.g., MI, CV death, revascularization) by three years. For initial sample size calculations, we have estimated 15-35% of our population would reach one of these endpoints. Sample size calculations with this dichotomous endpoint are displayed below.

Table 1. Treatment Effect Needed To Reach Significance Based on Event Rate

Event Rate Placebo Arm	Event Rate Treatment Arm	RR	Power*
15%	6.5%	2.3	80%
20%	10%	2.0	80%
25%	14%	1.8	80%
30%	18%	1.7	80%
35%	22.5%	1.6	80%

*Assumes a sample size of 225 patients per arm.

Table 2. Patients Needed or Study Power Assuming a 1.30 RR Treatment Effect

Event Rate Placebo Arm	RR	Study Power*	Fixing Power	Sample Size Required**
15%	1.3	20%	80%	1160
20%	1.3	25%	80%	955
25%	1.3	30%	80%	781
30%	1.3	35%	80%	651
35%	1.3	41%	80%	548

* Assuming a sample size of 225.

** Assuming a power of 80%.

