7.2 SCREENING VISIT

The study will be described to the potential participant and if she agrees to participate, an informed consent form should be reviewed and signed.

If creatinine and fasting triglycerides have been assessed within the past twelve months, no blood collection is necessary at this visit. If they are not available, the patient will be asked to fast for at least twelve hours prior to coming to clinic and a blood sample will be taken. This should be sent to the local laboratory for analysis of creatinine, triglycerides, FSH and INR, as necessary.

A general physical (including a mammogram, if none has been done in the last 12 months, a PAP smear and a pelvic examination) is to be completed. If a mammogram has been done within the past twelve months, the coordinator will obtain a medical release from the patient and obtain a copy of the results. For women participating in the Brachial Artery Reactivity Study (see appendix D) and the Effects of Hormone Replacement Therapy on Electrocardiographic and Scintigraphic Measures of Myocardial Ischemia Study (see appendix E) appropriate assessments will be performed. However, a woman who is otherwise eligible may refuse either or both of these studies and still be randomized into the WAVE trial.

Comment [TBC1]:

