10. STATISTICAL DESIGN AND ANALYSES

10.1 OVERVIEW OF STUDY DESIGN

The WAVE trial is a randomized double masked placebo controlled factorial clinical trial. The trial will randomize women to active or placebo HRT (estrogen or, when appropriate, estrogen with progesterone), and to active or placebo vitamin combination (1000mg/day of vitamin C and 800 IU/day of vitamin E). The trial will be conducted at five participating clinical centers and will randomize a total of 450 postmenopausal women with angiographically documented coronary artery disease. The primary objective of the WAVE trial is to determine whether hormone replacement or antioxidant therapy favorably affect coronary atherogenesis during approximately a three year study interval. Response to the treatments will be assessed by the mean, for each woman, of the changes in minimum lesion diameter (MLD), of study defined lesions, as estimated at baseline and at the exit angiogram, between the randomized treatment groups. Two null hypotheses will be tested in this trial:

1. There is no difference in average change in mean lesion diameter per year between women who receive hormone replacement therapy and women who receive placebo.
2. There is no difference in average change in mean lesion diameter per year between women who receive antioxidants and women who receive placebo.

Although both hypotheses will be tested, no adjustment will be made for multiple comparisons because the trial is powered to test both hypotheses at the 0.05 level.

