10.4 SAMPLE SIZE CALCULATIONS

The sample size calculations are based on a change in mean MLD using a t-test. The antioxidant and HRT components are treated as separate trials (no interaction is assumed). No adjustment for multiple comparisons will be made.

The type 1 error rate α was 0.05 (2-tailed). Although a rank test will be used, given the sample sizes contemplated in the study, the power of the rank test is essentially the same as that of the t-test under the assumption of normality. The power calculations are based on the effect size, defined as the expected difference in outcome between treatment and control divided by the

standard deviation of the outcome (the outcome here is the change in mean MLD between baseline and follow-up). The effect sizes for four published studies are summarized below.

STARS	FATS	SCRIP	MARS
0.86	0.51	0.29	0.14

The weighted average of these effect sizes, weighing by the number of patients in each study is 0.334. With this effect size and a power of 0.90, the required total sample size is N=380. Assuming a dropout rate of 15%, 450 patients are needed. If a 20% dropout rate is assumed, the power of the test for various effect sizes is summarized in the table below:

	N=450	N=425	N=400	N=375	N=350
ES=0.30	0.81	0.79	0.77	0.74	0.71
ES=0.35	0.91	0.90	0.88	0.86	0.83
ES=0.40	0.97	0.96	0.95	0.93	0.92

Based on these considerations, 400 patients is considered the minimum acceptable sample size for the study. The target sample size for the study is 450 patients.

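### The 80% power in Appendix E, Table 1 (dichotomous option) treats all 450 randomized women as evaluable, although the substudy is optional and the protocol itself plans for 15-20% dropout

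*Protocol*

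**What the plan says.** Section 18.7 (Appendix E) considers two forms of the substudy's primary endpoint, continuous and dichotomous, and gives calculations only for the second. The dichotomous version is introduced as "defining a successful therapy as one which prevented both the progression of ischemic territory or the occurrence of clinical endpoints", with MI, cardiovascular death and revascularization as examples of clinical endpoints, counted up to three years. On the expected frequency it says "we have estimated 15-35% of our population would reach one of these endpoints".

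Table 1 there, titled "Treatment Effect Needed To Reach Significance Based on Event Rate", lists placebo against treated rates of 15 v 6.5%, 20 v 10%, 25 v 14%, 30 v 18% and 35 v 22.5%, each with power 80%. Its footnote reads "Assumes a sample size of 225 patients per arm". Table 2 gives study power for a relative risk of 1.3, also at a sample size of 225.

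Three other places bear on that number:

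- Section 10.1: the trial "will randomize a total of 450 postmenopausal women with angiographically documented coronary artery disease".
- Section 7.2: "a woman who is otherwise eligible may refuse either or both of these studies and still be randomized into the WAVE trial". Section 18.4 adds only that every randomized woman will be approached about the substudy.
- Section 10.4: "Assuming a dropout rate of 15%, 450 patients are needed". The power table that follows in that section uses 20% dropout.

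**The concern.** With equal allocation to four groups, each factor compares 225 women with 225. The substudy's 225 per arm is therefore every woman in the trial. The main endpoint was given an allowance for dropout. The substudy, in the same women over about the same three years, was given none, and it has a further source of loss because women may decline it.

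A woman who declines the scans, or is lost before three years without a clinical event, cannot be classed as free of ischemic progression. She does not contribute to the comparison that Table 1 describes.

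These tables are the substudy's only power justification, and section 18.1 expects that outside funding will be needed. A funder would take the 80% as what the design is expected to deliver. The tabled effects are already large, with relative risks of 1.6 to 2.3, so a shortfall falls on a substudy that could detect only large effects to begin with.

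**Working it through.** **Inputs.** Rate pairs, 225 per arm and 80% power come from section 18.7. The 450 randomized come from section 10.1, and the 15% and 20% dropout from section 10.4. Section 18.7 gives no significance level, so I take the main trial's ("The type 1 error rate α was 0.05 (2-tailed") as an assumption. The protocol gives no uptake rate, so uptake is assumed and shown over a range.

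**Formula.** Two-proportion z-test with n per arm and p̄ the mean of the two rates:

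power = Φ{ [ |p1 − p2| − c − 1.96·√(2p̄(1−p̄)/n) ] / √([p1(1−p1) + p2(1−p2)]/n) }

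where c = 1/n with continuity correction and c = 0 without.

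**Reproducing Table 1.** For 20 v 10% at n = 225, the null standard error is √(0.255/225) = 0.03367 and the alternative standard error is √(0.25/225) = 0.03333. With correction: (0.1000 − 0.0044 − 0.0660)/0.03333 = 0.887, so power is 0.813. Over the five rows, corrected power is 0.790, 0.813, 0.809, 0.821 and 0.809. The n per arm needed for 80% is 231, 219, 221, 214 and 221. That matches the stated 80% at 225, allowing for rounded rates. The uncorrected formula gives 0.831-0.849, unpooled 0.836-0.853, arcsine 0.838-0.853 and one-sided 0.90-0.91; none of these gives 80%. Table 1 is thus consistent with the corrected formula when all 225 per arm are evaluable.

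**Evaluable number.** n per arm = 450 × uptake × (1 − dropout) / 2. For example, 450 × 1 × 0.85 / 2 = 191.25; 450 × 1 × 0.80 / 2 = 180; 450 × 0.80 × 0.80 / 2 = 144.

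**One row at 180 per arm (20 v 10%).** The standard errors are √(0.255/180) = 0.03764 and √(0.25/180) = 0.03727. With correction: (0.1000 − 0.0056 − 0.0738)/0.03727 = 0.555, so power is 0.710. Without correction it is 0.759.

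**All five rows (range).**

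| Uptake | Dropout | n per arm | Corrected | Uncorrected |
|---|---|---|---|---|
| 100% | 0% | 225 | 0.790-0.821 | 0.831-0.849 |
| 100% | 15% | 191 | 0.714-0.750 | 0.767-0.787 |
| 100% | 20% | 180 | 0.684-0.722 | 0.742-0.762 |
| 90% (assumed) | 15% | 172 | 0.661-0.700 | 0.723-0.743 |
| 90% (assumed) | 20% | 162 | 0.631-0.671 | 0.697-0.717 |
| 80% (assumed) | 15% | 153 | 0.602-0.643 | 0.672-0.692 |
| 80% (assumed) | 20% | 144 | 0.571-0.614 | 0.645-0.666 |

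**Table 2.** I read the relative risk of 1.3 as placebo rate over treated rate, with 225 per arm. The stated study powers are 20, 25, 30, 35 and 41%. The uncorrected formula gives 19.0, 24.9, 31.3, 38.3 and 45.7%; the corrected one gives 15.4, 21.1, 27.4, 34.3 and 41.7%. The uncorrected formula is closer in the first three rows and the corrected one in the last two. No single formula is established across section 18.7, which is why both columns are shown above.

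**The case against.** The strongest reply is that Table 1 contains no arithmetic error. It reproduces at its stated n, and the footnote discloses that n openly. That stands: the fault is a planning assumption that conflicts with sections 7.2 and 10.4, not a miscalculation.

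Several stronger readings are tempting, and the protocol does not support them.

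- A reader might infer that power is about 70% or less. At the base-case 15% dropout with full uptake it is 71-75% corrected and 77-79% uncorrected. A value of about 70% or lower needs 20% dropout under the corrected formula, or refusal at a rate the protocol does not give.
- A reader might infer that every woman must be scanned at three years. MI, cardiovascular death and revascularization are themselves events, so a woman who has one is evaluable without a final scan. The 15-20% was also set for the angiographic endpoint and may overstate loss for this composite.
- A reader might take the 80% as the power of the substudy as a whole. It covers only the dichotomous option. Section 18.6 leads with a regression on continuous defect size, and section 18.7 says the continuous endpoint needs fewer patients but gives no calculation for it.
- A reader might fear that a null result would be taken to exclude moderate effects. Table 2 already reports only 20-41% power for a relative risk of 1.3.
- Table 1's title speaks of reaching significance while the rows are effects detectable with 80% power. Its power column shows 80% in every row, so this is editorial.

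What survives all of this is that a number equal to the full cohort is used with no allowance for refusal or loss.

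**Conclusion.** The point holds for the dichotomous option. The stated 80% requires all 450 randomized women to be evaluable for the composite, and other sections of the protocol say this should not be expected. With full uptake and the protocol's own dropout, power for the tabled effects is 68-75% with the formula that reproduces Table 1, or 74-79% without continuity correction. It is below 80% either way before any refusal. With an assumed 80% uptake and 20% dropout it is 57-61% corrected, or about 65-67% uncorrected.

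This rests on three assumptions: a two-sided 0.05 test, borrowed from section 10.4; dropout for the composite similar to that planned for the angiographic endpoint; and, for the lower figures only, the assumed uptake. The matter is confined to an appendix substudy and does not touch the main trial's power.

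**What to change.** In section 18.7, restate Table 1 and the study-power column of Table 2 for the expected evaluable number per arm, 450 × uptake × (1 − dropout) / 2. Use the 15-20% dropout of section 10.4, or a separately justified figure for the composite, and show uptake as an assumed range. Name the test formula and significance level, and use one formula for both tables. State that the figures apply to the dichotomous option only. The sample-size column of Table 2 does not depend on how many women are available, so this point does not require it to change.

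The cost is a recalculation in Appendix E and less favourable stated figures. No extra enrolment or procedures are needed.

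### Appendix E, Table 2 is labelled RR 1.30, but its 15%, 20% and 25% rows were computed for RR 1.36, 1.33 and 1.32, so sample sizes are up to 26% too small

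*Protocol*

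**What the plan says.** Protocol section 18.7 (Appendix E, the SPECT and treadmill substudy) offers a dichotomous endpoint as an alternative to change in ischemic burden. For planning it says "we have estimated 15-35% of our population would reach one of these endpoints".

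Table 1 gives treated rates detectable with 80% power and carries the footnote "Assumes a sample size of 225 patients per arm". Its rows fix the direction of RR as placebo rate over treated rate: 20% against 10% is printed as 2.0.

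Table 2 is headed "Table 2. Patients Needed or Study Power Assuming a 1.30 RR Treatment Effect". Its columns are placebo rate, RR, power, fixed power and required sample size. The first three rows read "15% 1.3 20% 80% 1160", "20% 1.3 25% 80% 955" and "25% 1.3 30% 80% 781". The last two give 35% power and 651 at a 30% placebo rate, and 41% power and 548 at 35%. The footnotes are "Assuming a sample size of 225" for the power column and "Assuming a power of 80"% for the sample-size column.

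Table 2 prints no treated-arm rates. Section 18.7 states neither alpha nor the formula.

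**The concern.** At a 15% placebo rate, an RR of 1.30 means a treated rate of 15/1.30 = 11.54%, a difference of 3.46 percentage points. A required size of 1160 per arm looks too small for a difference that narrow. If the treated rates were rounded before the calculation, the rows with the lowest event rates suffer most, because half a percentage point is then a large share of the difference.

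The table would then describe an effect other than the one it names, and would understate how far the substudy is from detecting that effect. Section 18.1 says the substudy will probably need outside funding, so a funder may read these figures directly.

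**Working it through.** **Inputs**
- Placebo rates p = 15, 20, 25, 30, 35%; RR = p/q, where q is the treated rate (section 18.7).
- 225 per arm for the power column; 80% power for the sample-size column (section 18.7).
- Alpha 0.05 two-sided. This is an assumption carried over from section 10.4 of the main trial, because section 18.7 is silent.

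**Formulas**, with m = (p+q)/2 and d = p − q:
- Uncorrected: n₀ = [1.960·√(2m(1−m)) + 0.842·√(p(1−p)+q(1−q))]² / d²
- Continuity-corrected: n = (n₀/4)·[1 + √(1 + 4/(n₀d))]²
- Corrected power at n per arm: Φ{[(d − 1/n)√n − 1.960·√(2m(1−m))] / √(p(1−p)+q(1−q))}. Uncorrected power drops the 1/n.

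**Step 1: which method was used.** For Table 1 at 225 per arm, corrected power is 79.0, 81.3, 80.9, 82.1 and 80.9%. Uncorrected power is 83.1, 84.6, 84.0, 84.9 and 83.6%. The printed value is 80% throughout, so the corrected form fits better.

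**Step 2: reproduce Table 2.** First row with q = 11%: m = 0.13 and d = 0.04. The numerator is (0.9322 + 0.3996)² = 1.7735, so n₀ = 1.7735/0.0016 = 1108, and n = 1158 after correction. The printed figure is 1160. All rows, corrected, with whole-percent q:

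| p | q | RR = p/q | n per arm | printed | power at 225 | printed |
|---|---|---|---|---|---|---|
| 15% | 11% | 1.36 | 1158 | 1160 | 20.0% | 20% |
| 20% | 15% | 1.33 | 945 | 955 | 24.5% | 25% |
| 25% | 19% | 1.32 | 780 | 781 | 29.5% | 30% |
| 30% | 23% | 1.30 | 651 | 651 | 35.0% | 35% |
| 35% | 27% | 1.30 | 548 | 548 | 41.0% | 41% |

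Nine of the ten entries match to rounding or within two patients. The tenth (945 against 955) is about 1% off. The sample sizes match only as per-arm numbers.

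**Step 3: recompute at RR 1.30.** First row with q = 11.54%: m = 0.1327 and d = 0.03462. The numerator is (0.9403 + 0.4033)² = 1.8052, so n₀ = 1.8052/0.001198 = 1507, and n = 1564 after correction. All rows, corrected:

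| p | q = p/1.30 | n per arm | printed | printed n vs needed | power at 225 | printed |
|---|---|---|---|---|---|---|
| 15% | 11.54% | 1564 | 1160 | 26% too small | 15.4% | 20% |
| 20% | 15.38% | 1115 | 955 | 14% too small | 21.1% | 25% |
| 25% | 19.23% | 845 | 781 | 8% too small | 27.4% | 30% |
| 30% | 23.08% | 666 | 651 | 2% too small | 34.3% | 35% |
| 35% | 26.92% | 538 | 548 | 2% too large | 41.7% | 41% |

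At RR 1.30 the printed 1160 per arm gives 67% power and the printed 955 gives 73%.

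**Step 4: without the continuity correction, at RR 1.30.**
- Required n is 1507, 1072, 811, 637 and 513. The printed sizes are 23%, 11% and 4% too small in the first three rows, and slightly generous in the last two.
- 1160 per arm gives 69% power.
- Power at 225 per arm is 19.0, 24.9, 31.3, 38.3 and 45.7%.

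**Step 5: other readings.** One-sided alpha, 225 as a total, other variance forms (unpooled, arcsine, log RR, log OR), treated rates of 0.7p or 1.3p, and an odds ratio of 1.3 were also tried. None reproduces the table at the labelled effect.

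**The case against.** The strongest counter-argument concerns the power column. Because section 18.7 names no formula, one may use the uncorrected test. At RR 1.30 that gives 19.0, 24.9 and 31.3% in the first three rows, within 1.3 points of print, so power would not look overstated there. This stands as a caveat: the power claim depends on the continuity correction. But the uncorrected test misses the last two power entries by 3.3 and 4.7 points, matches none of the five sample sizes, and fits Table 1 less well. One corrected method accounts for both tables.

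Second, the RR column shows one decimal, and 1.33 and 1.32 round to 1.3. That excuses neither the heading, which says 1.30, nor the first row, where 1.36 rounds to 1.4. It is fair that the last two rows are essentially right.

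Third, the unit can be recovered: Table 1, directly above, says the 225 is per arm. The missing label is a minor point.

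Fourth, nothing is sized from this table. The dichotomous endpoint is an alternative, the main trial fixes recruitment at 450, and the printed power of 20 to 41% already shows the substudy is underpowered for this effect. That is correct and limits the consequences. The figures in the upper rows still do not correspond to the effect they are labelled with.

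**Conclusion.** The concern holds. The first three rows of Table 2 were computed for RRs of about 1.36, 1.33 and 1.32, most plausibly because treated rates were taken as whole percents. That cause is inferred, since the treated rates are not printed.

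At RR 1.30 the 15% row is short by 1564 − 1160 = 404 women per arm, and the next two rows by 160 and 64. The shortfall in the first two rows is substantial with or without the correction; in the 25% row it falls to 4% without it. The overstated power in the first three rows (4.6, 3.9 and 2.6 points) rests on the continuity-corrected method that best fits the document. All figures assume two-sided alpha of 0.05 and equal arms.

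Correcting the table strengthens its message that 225 per arm is far from adequate for an RR of 1.30.

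**What to change.** Correct Table 2 in one of two ways:

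1. **Keep RR 1.30 and recompute.** Power at 225 per arm becomes 15, 21, 27, 34 and 42%. Sample size per arm for 80% power becomes about 1564, 1115, 845, 666 and 538.
2. **Keep the printed figures and relabel.** Add a column with treated rates 11, 15, 19, 23 and 27%, give the RRs as 1.36, 1.33, 1.32, 1.30 and 1.30, change the heading, and check the 955 in the 20% row, which recomputes to 945.

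In either case, state the alpha, its sidedness and the formula, including whether a continuity correction was applied (the recomputed figures above assume two-sided 0.05 with the correction). Mark both the 225 and the sample-size column as per arm.

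The cost is an edit to one table and its footnotes in Appendix E. Design, conduct and the main trial are unaffected. Under the first option the figures in the first four rows become less favourable.

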18.8 DISCUSSION

Coronary artery disease is the number one cause of morbidity and mortality in women, however, the diagnosis of coronary disease in women is complicated. As many as 25-75% of women referred for evaluation of chest pain with insignificant disease will have either abnormal treadmill ECGs or abnormal perfusion imaging. This constellation of positive noninvasive testing with the presence of insignificant coronary disease may indicate dynamic functional stenoses (e.g., microvascular angina, or vasospastic angina), or may simply be false positive studies.

The overall outcome of this trial will be to characterize the ability of hormone replacement therapy and antioxidants to slow the progression of coronary artery disease as assessed by luminal diameter at catheterization. However, angiographic changes are often minimal in regression trials despite marked improvement in patient outcomes. This is due to difficulties in quantification of angiographic stenoses, to the development of more stable plaques, and potentially to the differences in vasomotor tone between normal and diseased vessels. A recent study looked at changes in nuclear perfusion imaging with short term fluvastatin therapy (cholesterol lowering agent). They found a 30% decrease in ischemic territory by perfusion imaging with a drug thought to improve vascular function and known to improve clinical outcome. The current substudy will characterize the effects of treatment on the patient's

ischemic burden with exercise nuclear perfusion imaging. Nuclear perfusion imaging will provide an additional method by which to quantify changes in coronary atherosclerosis and function, and to correlate changes in ischemia with improvements in luminal diameter and patient outcome.

Therefore, in this substudy, by obtaining stress myocardial perfusion images at enrollment, three month return visit, and trial conclusion, we propose to study the effects of study drugs on symptoms, ischemia, functional status, and outcomes. In comparison to the enrollment test, the three month exercise perfusion test will give data on the acute effects of drug on vasomotor tone, exercise duration, and positive ECG responses to exercise. The performance on the initial perfusion scan will be correlated with subsequent cardiac event rates to determine its predictive ability. Finally, the three year perfusion test will yield information on the progression of coronary artery disease by evaluating improvement in degree of ischemia.

